2.2.1 Randomization and drug dispensing irregularities

Randomization and drug-dispensing irregularities occur whenever:

1. A randomization is not in accordance with the protocol-defined randomization method, such as a) an ineligible patient is randomized, b) a patient is randomized based on an incorrect stratum, c) a patient is randomized twice, or d) in a dynamic randomization scheme the treatment assignment is, in fact, not random, due to a computer program error.

OR

2. A patient is dispensed an IMP kit not allocated by the protocol-defined randomization, such as a) a patient at any time in the study is dispensed a different treatment kit than as randomized (which may or may not contain the correct-as-randomized IMP), or b) a nonrandomized patient is treated with IMP reserved for randomized patients.

Randomization and drug-dispensing irregularities will be monitored throughout the study and reviewed on an ongoing basis.

The major or critical randomization and drug-dispensing irregularities will be documented in the clinical study report. If the number of irregularities is large enough to make a tabular summary useful, the irregularities will be categorized and summarized among randomized patients (number and percentages). Nonrandomized, treated patients will be described separately.

Randomization and drug-dispensing irregularities to be prospectively identified include but are not limited to:

- Kit dispensation without IRT transaction
- Erroneous kit dispensation
- Randomization by error
- Patient randomized twice
- Stratification error

2.3 ANALYSIS POPULATIONS

Patients who are dispensed study drug without calling the IRT or before calling the IRT are considered nonrandomized patients. They are excluded from any population for analysis, including safety. However, if these patients experienced any significant safety event, they should be documented separately in the clinical study report.

The randomized population includes any patient who has been allocated to a randomized treatment regardless of whether the treatment kit was used.

For any patient randomized more than once, only the data associated with the first randomization will be used in any analysis population. The safety experience associated with any later randomization will be assessed separately.

2.3.1 Efficacy populations

The primary efficacy analysis population will be the ITT population as defined in the protocol.

2.3.1.1 Intent-to-treat population

The primary efficacy population will be the ITT population, which includes all randomized patients, irrespective of compliance with the study protocol and procedures.

Patients will be analyzed for efficacy analyses in the treatment group to which they are randomized.

2.3.1.2 Per-protocol population

The Per-Protocol population is a subset of the ITT population, which includes all randomized and exposed patients, who do not permanently discontinue IMP allocated by randomization or do not switch from treatment group during the main 6-month period, who perform week 26 and who do not present major or critical protocol deviations that could impact the analysis during the main 6-month period. The major and critical protocol deviations excluding from the per protocol population are defined as:

- Missing baseline HbA1c value.
- No Visit 9 (Week 26) HbA1c value.
- Use of any insulin other than IMP or non-IMP for 10 days or more during the main 6-month treatment period.
- T1DM patients:
 - Use of any non-insulin glucose lowering agents during the main 6-month treatment period.
- T2DM patients:
 - Use of any non-insulin glucose lowering agents (except continuation of pre-study oral antidiabetic treatments at a stable dose) during the main 6-month treatment period.
 - Use of sulfonylureas and glinides during the main 6-month treatment period.
- Use of systemic glucocorticoids greater than replacement dose for more than 10 days during the main 6-month treatment period.
- Initiation of weight loss drugs during the main 6-month treatment period.
- Wrong randomization stratum of type of diabetes (T1DM, T2DM).
- Patients who met any of the following exclusion criteria:
 - E02: HbA1c <7% or >10% at screening.
 - E08: At screening visit, body mass index (BMI) \geq 35 kg/m2 in patients with T1DM and \geq 40 kg/m2 in patients with T2DM.

- E18: Use of investigational drugs or prohibited therapy for this study within 3 months or 5 half-lives, whichever is longer, prior to the screening visit.
- E19: limited to the following conditions:
 - o status post pancreatectomy
 - \circ status post pancreas and/or islet cell transplantation
- Serious GCP misconduct.

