- E 14. Patients with severe or unstable hepatic, gastrointestinal, cardiovascular (including congestive heart failure New York Heart Association [NYHA] III/IV, history of myocardial infarction, stroke or heart failure requiring hospitalization in the last 3 months prior to screening visit), respiratory, neurological, psychiatric, hematological, renal, endocrine, dermatological disease, active malignant tumor, other major systemic disease or patients with short life expectancy or any other medical condition that might interfere with the evaluation of study medication according to Investigator's medical judgment.
- E 15. Any clinically significant abnormality identified on physical examination, laboratory tests or ECG that in the judgment of the Investigator or any subInvestigator would preclude safe completion of the study or constrains efficacy assessment.
- E 16. Known history of drug or alcohol abuse within 6 months prior to the time of screening.
- E 17. Participation or planned participation in another clinical study other than disease registries.
- E 18. Use of investigational drugs or prohibited therapy for this study within 3 months or 5 half-lives, whichever is longer, prior to the screening visit.

E 19. Conditions/situations such as:

- Status post pancreatectomy,
- Status post pancreas and/or islet cell transplantation,
- History of severe hypoglycemia requiring Emergency Room admission or hospitalization in the last 3 months before screening visit,
- Hospitalization for recurrent diabetic ketoacidosis (DKA) in the last 3 months before screening visit,
- Patients with conditions/concomitant diseases making them non evaluable for the primary efficacy endpoint (eg, hemoglobinopathy or hemolytic anemia, receipt of blood products within the last 3 months prior to the screening visit); any anemia with anticipated rapid correction,
- Patients with conditions/concomitant diseases precluding their safe participation in this study (unstable proliferative diabetic retinopathy or any other rapidly progressive diabetic retinopathy or macular edema likely to require treatment [eg, laser, surgical treatment or injectable drugs, etc]) during the study period,
- No latest exam by an ophthalmologist (US/Canada: ophthalmologist or optometrist) within 12 months for patients with retinopathy or within 24 months for those with no evidence of retinopathy (exam during the screening period is acceptable, too),

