9.1 PRIMARY ENDPOINT

The primary endpoint is change in HbA1c (%) from baseline to Week 26.

For assessment methods refer to Section 9.2.2.2.1.

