11.3.1.2 Per protocol population

The Per Protocol population is a subset of the ITT population, which includes all randomized and exposed patients, who do not permanently discontinue IMP allocated by randomization during the main 6-month period, who perform Week 26 and who do not present major or critical protocol deviations that could impact the analysis during the main 6-month period. The major and critical protocol deviations will be detailed in the SAP.

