2.4.4.1.3 Supportive analysis

In the case the per-protocol population will represent less than 95% of the ITT population, a supportive analysis will be conducted on the per-protocol population to evaluate the robustness of the conclusion of the primary efficacy analysis when excluding the patients that may increase the chance of reaching non inferiority conclusion.

Data in the per-protocol population will be analyzed using an ANCOVA of the change in HbA1c from baseline to Week 26, including the fixed categorical effects of treatment group (SAR341402, NovoLog/NovoRapid), the randomization strata of geographical region and type of diabetes (Europe T1DM, US T1DM, US T2DM, Japan T1DM) and prior use of NovoLog/NovoRapid (Yes, No), as well as the continuous fixed covariate of baseline value.

The adjusted LS mean of the change in HbA1c from baseline to Week 26 for each treatment group (SAR341402, NovoLog/NovoRapid) will be estimated, as well as the between-group LS mean difference of SAR341402 versus NovoLog/NovoRapid, with the corresponding standard errors and 2-sided 95% CIs. These values will be calculated using the observed proportions of patients in the randomization strata and the observed baseline mean HbA1c in the PP population.

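### The SAP's per-protocol exclusions leave out the E19 item on HbA1c evaluability, so patients who breach it stay in the supportive HbA1c analysis

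*SAP*

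**What the plan says.** Protocol 9.1: "The primary endpoint is change in HbA1c (%) from baseline to Week 26".

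Protocol 7.2.1, criterion E19, bars a group of patients because their HbA1c cannot be relied on: "Patients with conditions/concomitant diseases making them non evaluable for the primary efficacy endpoint (eg, hemoglobinopathy or hemolytic anemia, receipt of blood products" in the 3 months before screening. The same bullet adds "any anemia with anticipated rapid correction".

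Protocol 11.3.1.2 removes patients with major or critical deviations capable of affecting the analysis and leaves the detail to the SAP: "The major and critical protocol deviations will be detailed in the SAP".

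SAP 2.3.1.2 supplies the list. It opens with "The major and critical protocol deviations excluding from the per protocol population are defined as" and cites four exclusion criteria: E02, E08, E18 and E19. The E19 entry reads "E19: limited to the following conditions", followed by pancreatectomy and pancreas or islet transplantation only.

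SAP 2.4.4.1.3 runs a per-protocol ANCOVA of HbA1c change if that population is below 95% of ITT. Its stated aim is to test robustness when "excluding the patients that may increase the chance of reaching non inferiority conclusion".

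**The concern.** The protocol says that one class of patients cannot be evaluated on the primary endpoint. The SAP then defines a population meant to be free of deviations that could affect the analysis of that endpoint, and keeps that class in. The same list removes a patient for BMI (E08), although a high BMI does not make HbA1c unusable.

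The direction matters in a non-inferiority trial. If HbA1c does not track glycemia in some patients in both arms, those patients contribute no treatment difference and pull the estimate towards zero. That favors a non-inferiority conclusion, which is what the supportive analysis is meant to guard against.

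**Working it through.** **1. Does any other entry in SAP 2.3.1.2 remove these patients?**

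- E02 (screening HbA1c range) and E08 (BMI) do not address whether HbA1c is valid.
- E18 covers investigational drugs and prohibited therapy. Blood products are not among the prohibited therapies in protocol 8.8.1.
- The entries for missing baseline or Week 26 HbA1c do not apply. These patients have a value; its validity is what is in doubt.
- E15, which mentions abnormalities that constrain efficacy assessment, is not on the list.
- The general phrase about deviations affecting the analysis does not rescue them. The next sentence defines those deviations by a closed list, and the E19 entry is expressly restricted.

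So a patient who breaches only the evaluability item stays in.

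**2. The plan's own power figure.** Inputs from SAP 1.3: 290 per arm, SD 1.0%, margin 0.3%, true difference 0. SAP 2.4.4.1.1 gives one-sided alpha 0.025.

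- SE = 1.0 × √(2/290) = 0.0830
- Power = Φ(0.3/0.0830 − 1.96) = 0.951 (stated: at least 95%)
- Both directions: 2 × 0.9508 − 1 = 0.902 (stated: at least 90%)

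Both reproduce. They concern the primary analysis, and the E19 entry does not enter them.

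**3. When the supportive analysis runs.** 95% of 580 is 551, so at least 30 patients must be outside the per-protocol population (550/580 = 94.8%). With 276 per arm, 552/580 = 95.2% and it does not run. Keeping E19 violators in makes the trigger very slightly harder to reach.

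**4. Size of the dilution.** Assumptions not in the documents: a fraction f of per-protocol patients in both arms has wholly uninformative HbA1c; SD stays 1.0%; the true difference equals the margin.

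- Expected difference = 0.3 × (1 − f)
- One-sided type I error = Φ(0.3 × f / SE − 1.96), with SE = √(2/n)

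| f | Expected difference (%) | Type I error, n = 290 per arm | n = 275 | n = 261 |
|---|---|---|---|---|
| 0 | 0.3000 | 0.0250 | 0.0250 | 0.0250 |
| 0.5% | 0.2985 | 0.0261 | 0.0260 | 0.0260 |
| 1% | 0.2970 | 0.0272 | 0.0271 | 0.0271 |
| 2% | 0.2940 | 0.0295 | 0.0294 | 0.0293 |
| 5% | 0.2850 | 0.0376 | 0.0372 | 0.0368 |

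In patient numbers, 2 to 5 per arm out of 275 gives f = 0.7% to 1.8%, a shift of 0.3 × f = 0.002 to 0.005 percentage points. The standard error at 275 per arm is √(2/275) = 0.085.

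**The case against.** **No decision rests on this.** Non-inferiority is concluded from the ITT population, which includes every randomized patient by definition. The per-protocol analysis is supportive and conditional. This stands, and it sets the severity.

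**The list is the SAP's to write.** A reader might infer that the SAP contradicts the protocol. It does not: protocol 11.3.1.2 delegates the list, and the restrictive wording on E19 shows a deliberate selection. What remains is an inconsistency with the population's aim, with no reason given. A possible reason is that the two retained conditions are plain history facts, whereas the evaluability item is open-ended and needs judgement in an open-label trial. That argues for blinded case review rather than for omission.

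**Breaches should be rare and visible.** Eligibility is checked at Visits 1 and 3. SAP 2.2.1 treats randomizing an ineligible patient as an irregularity to be monitored, and SAP 2.2 summarizes critical or major deviations by arm. This makes an unnoticed effect less likely but does not repair the list.

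**A one-arm artefact is not the right model.** A reader might picture several violators in one arm, all with a spurious HbA1c change in the same direction, and obtain a larger shift. E19 is applied before randomization, so no imbalance between arms is expected. An upward artefact in the SAR341402 arm would also make non-inferiority harder to show. The documents support only the two-arm dilution.

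**Conclusion.** The omission is real on the text. A patient randomized in breach of the E19 evaluability item, and otherwise compliant, stays in the per-protocol HbA1c analysis, against that population's own aim.

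The expected effect is small. For an assumed 0.5% to 2% of patients in both arms, the one-sided type I error of the supportive analysis rises from 0.025 to about 0.026 to 0.030. The documents give no number of such breaches, so the fractions are illustrative. Wholly uninformative HbA1c is the extreme case: partial information would mean less shrinkage, and any added variability would widen the interval and work against non-inferiority.

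A reader might infer that the trial's non-inferiority claim or its power is in doubt. The documents do not support that, because both rest on the ITT analysis. Severity is minor. Confidence is high for the textual gap but not for any material impact.

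**What to change.** Before the 6-month database lock, extend the E19 entry in SAP 2.3.1.2 to include the protocol's pre-randomization item on conditions that make a patient non-evaluable for HbA1c: hemoglobinopathy or hemolytic anemia as examples, blood products in the 3 months before screening, and anemia expected to correct rapidly. State that cases are identified from medical history and prior medication without knowledge of treatment arm. SAP 2.1.2 already defines prior medication to cover the 3 months before screening. If the sponsor prefers to leave the item out, the SAP should say why.

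Do not extend the exclusion to anemia or transfusion arising after randomization. E19 is an entry criterion and blood products are not a prohibited therapy during treatment. Such a rule would not follow from the protocol and would select on post-randomization events.

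Cost: one SAP line, some blinded case review, and a few fewer per-protocol patients. No new data are needed.

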2.3.2 Safety population

The safety population is defined as all randomized patients who receive at least one dose of IMP, analyzed according to the treatment actually received.

In addition:

- If a patient is dispensed IMP and is lost to follow-up without any documented evidence whether or not the patient took IMP, the patient will be considered exposed and included in the safety population.
- Randomized patients for whom it is unclear whether they took the study medication will be included in the safety population as randomized.
- Non-randomized but treated patients will not be part of the safety population, but their safety data will be presented separately.
- For patients receiving more than one study treatment during the trial, the patient will be analyzed in the treatment group in which he/she has mostly taken.

2.3.3 Anti-insulin antibody population

The AIA population is defined as all patients from the safety population with at least one AIA sample available for analysis (sample collected at least 8 hours after the last administration of mealtime insulin) during the on-treatment period, analyzed according to the treatment actually received.

2.4 STATISTICAL METHODS

Continuous data will be summarized by treatment group using the number of observations available (N), mean, SD, minimum, median, and maximum.

Categorical and ordinal data will be summarized using the number and percentage of patients in each treatment group.

In general, descriptive statistics of quantitative efficacy and safety parameters (result and change from baseline) by scheduled post-baseline visits will be provided on observed cases, ie, including only patients having non-missing assessments at a specific visit. All statistical analyses

(descriptive statistics, plots, and statistical models) will be performed on visits defined using the time windows provided in Section 2.5.4.

Statistical analyses will be performed on the overall study population regardless the type of diabetes, and pooling data from the patients treated with NovoLog and NovoRapid in the comparator group. For descriptive purpose, subgroup analyses may be conducted by type of diabetes (T1DM, T2DM) and by type of comparator used (NovoLog [in US], NovoRapid [in EU and Japan]), as described in the sections below.

2.4.1 Demographics and baseline characteristics

Parameters will be summarized on the randomized population analyzed in the treatment group to which they were randomized.

Parameters described in Section 2.1.1 will be summarized by treatment group and in overall treatment groups using descriptive statistics.

Medical/surgical history will be summarized by primary SOC and HLT in each treatment group and overall. Events will be sorted by SOC internationally agreed order and decreasing frequency of HLT based on incidence in the overall treatment group.

No statistical test for the between-group difference will be performed.

Demographics and baseline characteristics will also be presented according to the type of comparator (NovoLog, NovoRapid) and for T1DM patients.

2.4.2 Prior or concomitant medications

The prior, concomitant and post-treatment medications will be presented on the randomized population, separately for anti-diabetic medications and non-anti-diabetic medications. Anti-diabetic medications will be identified by a pre-defined list of ATC codes (see Appendix A).

Medications will be summarized by treatment group and overall (only for prior medications) according to the WHO-DD dictionary. Non-anti-diabetic medications will be summarized considering the first digit of the ATC class (anatomic category) and the first 3 digits of the ATC class (therapeutic category). All ATC codes corresponding to a medication will be summarized, and patients will be counted once in each ATC category (anatomic or therapeutic) linked to the medication. Therefore patients may be counted several times for the same medication. Anti-diabetic medications will be presented by pharmacological class (ATC3), chemical class (ATC4), and standardized medication name.

The tables for prior medications will be sorted by decreasing frequency within the ATC categories presented based on the overall incidence across treatment groups. In case of equal frequency, alphabetical order will be used.

The tables for concomitant and post-treatment medications will be sorted by decreasing frequency within the ATC categories presented based on the incidence in the SAR341402 group. In case of equal frequency, alphabetical order will be used.

Frequency statistics including number of patients and percentage will be provided. No statistical test for the between-group difference will be performed.

The prohibited medications will be presented by prohibited medication category (as defined in protocol deviations) and standardized medication name. The following prohibited medication categories will be presented:

- Use of any insulin other than IMP or non-IMP for 10 days or more during the treatment period.
- T1DM patients:
 - Use of any non-insulin glucose lowering agents during the treatment period.
- T2DM patients:
 - Use of any non-insulin glucose lowering agents (except continuation of oral antidiabetic treatments at a stable dose) during the treatment period
 - Use of sulfonylureas during the treatment period
- Use of systemic glucocorticoids greater than replacement dose for more than 10 days during the treatment period.
- Insulin pump therapy.
- Initiation of body weight loss drugs during the treatment period.
- Any other investigational product (ie, participation in another clinical trial).

Concomitant and prohibited medications will be presented for the main 6-month and for the 12-month period separately, and for T1DM patients.

2.4.3 Extent of investigational medicinal product exposure and compliance

The extent of IMP exposure will be assessed and summarized by actual treatment within the safety population (Section 2.3.2).

2.4.3.1 Extent of investigational medicinal product exposure

The extent of IMP exposure will be assessed by the duration of the open-label IMP exposure and daily insulin doses (basal, mealtime, total).

The exposure will be presented overall then by subgroups defined by the randomization strata of geographical region (Europe, US, Japan), type of diabetes (T1DM, T2DM) and type of comparator (NovoLog, NovoRapid).

Observation period

The observation period for exposure data will be defined as follows:

- The main 6-month on-treatment period is defined as the time from first injection of IMP up to Week 26 (Visit 9) or up to the day of last injection of IMP, whichever comes earlier.
- The 12-month on-treatment period is defined as the time from the first injection of IMP up to the day of last injection of IMP.

The exposure parameters will be provided separately for the main 6-month on-treatment period and for the 12-month on-treatment period.

Duration of exposure

The duration of exposure will be the total number of days of administration of the open-label IMP, ignoring temporary drug discontinuation (see Section 2.5.3 for calculation in case of missing or incomplete data).

The duration of exposure to the open-label IMP will be defined as:

(Date of the last IMP administration – date of the first IMP administration) + 1

The process described in Section 2.5.3 will be applied to define the date of the last IMP administration for the main 6-month on-treatment period and 12-month on-treatment period. If this date is missing, the IMP exposure duration should be left as missing.

Duration of IMP exposure will be summarized descriptively as a quantitative variable (number, mean, SD, median, minimum, and maximum). The number (n) and proportion (%) of patients exposed to the open-label IMP will be presented by specific time periods for each treatment group in the safety population.

The time periods of interest for the main 6-month on-treatment period are grouped as follows:

- Up to 4 weeks,
- >4 to 8 weeks,
- >8 to 12 weeks,
- >12 to 20 weeks,
- >20 to 25 weeks,
- >25 to 26 weeks,
- >26 weeks.

The time periods of interest for the 12-month on-treatment period are grouped as follows:

- Up to 4 weeks,
- >4 to 8 weeks,
- >8 to 12 weeks,
- >12 to 20 weeks,
- >20 to 26 weeks,
- >26 to 34 weeks,
- >34 to 40 weeks,
- >40 to 51 weeks,
- >51 to 52 weeks,
- >52 weeks.

The cumulative duration of exposure for the main 6-month on-treatment period will be described using the following time periods:

- $\geq 1 \text{ day},$
- > 4 weeks,
- > 8 weeks,
- > 12 weeks,
- > 20 weeks,
- > 25 weeks,
- > 26 weeks.

The cumulative duration of exposure for the 12-month on-treatment period will be described using the following time periods:

- $\geq 1 \text{ day},$
- > 4 weeks,
- > 8 weeks,
- > 12 weeks,
- > 20 weeks,
- > 26 weeks,
- > 34 weeks,
- > 40 weeks,
- > 51 weeks,
- > 52 weeks.

Daily insulin doses

The process described in Section 2.5.4 will be applied to assign visits to the insulin doses transferred from the e-diary webportal into the clinical database, and to retrieve doses in case of premature treatment discontinuation.

At baseline, the daily basal, mealtime, and total (basal plus mealtime) insulin doses (U and U/kg body weight) will be calculated as defined in Section 2.1.1. At Visit 3, daily insulin doses (basal, mealtime, and total) will be calculated as the median of daily insulin doses available in the week after the day of first IMP. At further visits, the daily insulin doses (basal, mealtime, and total) will be calculated as the median of daily insulin doses (basal, mealtime, and total) will be calculated as the median of daily insulin doses (basal, mealtime, and total) will be calculated as the median of daily insulin doses available in the week before the visit. Technical details related to the computation and handling of missing data are described in Section 2.5.

The daily insulin doses (basal, mealtime, total) will be described at baseline, during the week after the date of the first IMP administration, then at each visit, and the changes from baseline will be presented.

